## 2.3 BASELINE EVALUATION

### 2.3.1 Laboratory studies

To be performed at any time before protocol enrollment:

- HLA typing

To be performed within 16 days prior to protocol enrollment:

- Screening tests noted above will be used as baseline

Additional baseline labs to be performed

- ANA titer
- CD4:CD8 ratio, CD3, 4, 8, 19 subsets and NK markers (baseline, about day 29 prior to vaccination and around day 85, and then every 85 days thereafter while patients remain on study for follow-up)

### 2.3.2 Electrocardiogram (ECG) within 28 days prior to protocol enrollment

### 2.3.3 Scans and X-rays:

To be performed within 28 days prior to the protocol enrollment (may include based on site of disease):

- Computerized tomography (CT) of the chest/abdomen/pelvis
- Brain MRI
- PET scan
- Bone scan

## 2.4 REGISTRATION PROCEDURES

Authorized staff must register an eligible candidate with NCI Central Registration Office (CRO) within 24 hours of signing consent. A registration Eligibility Checklist from the web site (<http://home.ccr.cancer.gov/intra/eligibility/welcome.htm>) must be completed and sent via encrypted email to: NCI Central Registration Office (HOIS) [[contact]](mailto:[contact]). After confirmation of eligibility at Central Registration Office, CRO staff will call pharmacy to advise them of the acceptance of the patient on the protocol prior to the release

**Confidential**

*Abbreviated Title: Phase I MVA-Brachyury-TRICOM*

*Version Date: September 14, 2016*

of any investigational agents. Verification of Registration will be forwarded electronically via e-mail to the research team. A recorder is available during non-working hours.

### **3 STUDY IMPLEMENTATION**

#### **3.1 STUDY DESIGN**

This is an open-label phase I trial with sequential cohorts of patients (3–6 patients per dose cohort to establish safety) with dose escalation of MVA-brachyury-TRICOM vaccine (see Section 8). Three cohorts will receive MVA-brachyury-TRICOM vaccine administered subcutaneously as either 1, 2, or 4 injections of study drug (1 injection =  $2 \times 10^8$  IU) at monthly (28 days– 4 days up to +14 days) intervals for 3 months (treatment). A dose will be considered missed if not given within 14 days of the original schedule and the patient will resume treatment with the next scheduled dose. The time of patient monitoring post injection would be 2 hour observation after first dose and 30 minutes after subsequent doses.

Toxicity in the 28 days following the first vaccination after the 3rd subject (or 6th subject, if applicable) in dose levels 1 through 3 will be employed for decision-making (i.e., for dose-escalation and for maximum tolerable dose estimation). Inpatient dose escalation will not be allowed. In addition, patients may be enrolled as an expansion cohort at the MTD and at the dose level just below the MTD after either 0 of 3 or no more than 1 of 6 patients have been treated at that dose level and have not experienced a DLT for at least 28 days. Cohorts 2 and 3 will accrue up to an additional 10 evaluable patients each (up to 16 patients total in each) for safety and correlative analysis.

Patients will be sequentially enrolled and monitored for safety as described at dose level 2 and dose level 3. If 0 of 3 or no more than 1 of 6 patients treated at each dose level have experienced a DLT for at least 28 days, we will enroll patients on the expansion phases.

Patients may be concurrently enrolled in the expansion cohort of dose level 2 while enrolling patients on dose level 3 for safety evaluation. Any patient who is eligible will be prioritized into a dose escalation slot. Once all dose escalation slots are filled, patients will be enrolled sequentially onto the expansion phase 2, followed by phase 3. Expansion slots will only be filled by subjects who are not eligible (due to concurrent therapy) for escalation slots until safety is established in both dose level 2 and 3. There will not be randomization.

Patients who come off study for any reason other than IND-related toxicity (defined as at least possibly related) prior to completion of the first restaging evaluation (about day 85) may be replaced. If a patient did not experience DLT and did not complete the DLT evaluation period (28 days), he or she will not be evaluable for toxicity and will be replaced in the dose level as outlined in Statistical Design (Section 8).

- If 0/3 patients develop DLT on a dose level, then the dose may be escalated. For purposes of obtaining additional safety and efficacy information, cohorts up to 6 patients/cohort may be enrolled.
- If 1/3 patients develops DLT on a dose level, then up to 3 more patients will be enrolled.
- If no more than 1/6 patients develops DLT, then the dose will be escalated.

**Confidential**

*Abbreviated Title: Phase I MVA-Brachyury-TRICOM*

*Version Date: September 14, 2016*

- If 2 or more patients experience DLT on a dose level, then the MTD has been exceeded and dose escalation has been completed. Three patients will be enrolled on the dose level below that level, provided that not more than 3 patients were treated on that dose level.

(The MTD will be the dose level at which no greater than 1/6 patients has a DLT, and the next higher dose level has at least 2 patients with a DLT.)

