**Confidential**

*Abbreviated Title: Phase I MVA-Brachyury-TRICOM*

*Version Date: September 14, 2016*

Number of Patients with DLT at a Given Dose Level	Escalation Decision Rule
0 of 3	Enter up to 3 patients at the next dose level
$\geq 2$	Dose escalation will be stopped. This dose level will be declared the maximally administered dose (highest dose administered). Up to three (3) additional patients will be entered at the next lowest dose level if only 3 patients were treated previously at that dose.
1 of 3	Enter up to 3 more patients at this dose level. 
 
• If 0 of these 3 patients experience DLT, proceed to the next dose level.
 
• If 1 or more of this group experience DLT, then dose escalation is stopped, and this dose is declared the maximally administered dose. Up to three (3) additional patients will be entered at the next lowest dose level if only 3 patients were treated previously at that dose.
 

$\leq 1$ of 6 at highest dose level below the maximally administered dose	This is the MTD and is generally the recommended phase II dose. At least 6 patients must be entered at the recommended phase II dose.

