## **8 STATISTICAL CONSIDERATIONS**

This study will be conducted as a standard phase I trial with an expanded cohort at the MTD. There are 3 dose levels of vaccine to be evaluated, and initially 3 patients will be enrolled in the lowest dose level. If 0/3 have a dose limiting toxicity (DLT) after 28 days from the third patient receiving the initial vaccine on study, then subsequent patients will be accrued to the next higher dose level. If 1/3 has a DLT, then 3 additional patients will be enrolled at that dose level. If 1/6 has a DLT, escalation may proceed, while if 2+/6 have a DLT, then the MTD will be considered to have been exceeded, and up to 3 additional patients will be enrolled at the next lower dose level if 6 patients have not previously been enrolled at that dose. The MTD will be the dose level at which no greater than 1/6 patients has a DLT, and the next higher dose level has at least 2 patients with a DLT.

The MTD will initially consist of 6 patients as indicated, and the study plans to enroll a total of 10 additional patients each at the MTD and the dose level below MTD (total of 16 at the MTD and up to 16 at the dose level just below the MTD) in an effort to identify significant changes in T-cell precursors will be detectable. Potential evaluation techniques include flow-cytometry based intracellular cytokine staining after bBrachyury 15-mer stimulation and ELISPOT. Evaluations will take place both with respect to absolute change as well as whether a positive response is identified.

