Because we will be using new evaluation techniques with a first in human study, we will enroll 10 patients in an expansion cohort, resulting in 16 potential evaluable patients in the two highest tolerated dose level cohorts, which will provide 80% power to detect a change in T-cell precursors from baseline equal to 1.0 standard deviations of the difference (effect size = 1.0) using a 2-tailed 0.05 alpha level paired t-test. All 10-16 patients in each dose level with evaluable T-cell precursor data at this dose level will be included in the analysis, with 10 patients providing an illustration of 80% power based on that minimal number. The actual power could be greater than 80% if 11-16 patients are evaluable for this determination. In practice, a nonparametric Wilcoxon signed rank test will be used. A positive response using the flow based intracellular cytokine staining assay will be defined as the frequency of T lymphocytes positive for a cytokine or CD107a post-vaccine being increased greater than two-fold compared to both (1) pre-vaccine values and (2) HLA control post-vaccine; the fraction of the patients who have a positive response out of those evaluable for this determination will be noted and reported along with a corresponding 95% confidence interval.

Although the MTD will have been declared after 6 patients at that dose level have been evaluated, monitoring for toxicity in the additional cohort of patients will continue. In the event that more than one third of all patients enrolled at the MTD experience a DLT, protocol modifications will be undertaken to reduce the likely level of toxicity in future patients prior to continuing to enroll additional subjects.

Clinical response evaluation will take place in the patients enrolled at the MTD and the expansion cohort. The results will be considered secondary and will be used to determine the parameters for a subsequent phase II trial should the preliminary findings from this trial warrant further investigation.

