**Confidential**

*Abbreviated Title: Phase I MVA-Brachyury-TRICOM*

*Version Date: September 14, 2016*

Up to 18 patients may be required to be enrolled in the 3 cohorts, plus an additional 10 at the MTD and the next highest dose level. Thus, up to 38 patients may be theoretically required to complete this trial. If 3 patients per month can be accrued, the study is expected to require 1 year to complete the necessary enrollment.

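### The rule for adding patients at the level below a stopped dose differs between Sections 3.1/3.1.3 and Section 8 when that level already holds 4 or 5 patients

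*Combined protocol and SAP*

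**What the plan says.** Three places say what to do at the next lower level once a level has at least two DLTs.

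- Section 3.1, end of the escalation bullets: "Three patients will be enrolled on the dose level below that level, provided that not more than 3 patients were treated on that dose level".
- Section 3.1.3, decision table: up to three more patients at the next lowest level "if only 3 patients were treated previously at that dose". The last row of the same table states: "At least 6 patients must be entered at the recommended phase II dose".
- Section 8: "up to 3 additional patients will be enrolled at the next lower dose level if 6 patients have not previously been enrolled at that dose".

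Elsewhere, the size on which the MTD rests is stated consistently. Sections 3.1 and 8 define the MTD by no more than 1/6 with a DLT. Section 8 adds "The MTD will initially consist of 6 patients as indicated" and, on the expansion, "Although the MTD will have been declared after 6 patients at that dose level have been evaluated". The running text of Section 3.1.3 is looser and speaks of one DLT in up to six.

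On who counts, Sections 3.1 and 3.1.3 deal with a patient who has no DLT but does not complete 28 days: "he or she will not be evaluable for toxicity and will be replaced in the dose level". Both refer to Section 8 for the details, but Section 8 contains no replacement rule. Section 3.1 also lets a level that shows 0/3 be enlarged to as many as six, and lets the level 2 expansion run while level 3 is being tested.

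**The concern.** The add-back rule is the step that confirms the MTD after a level is stopped, and so the usual recommended phase II dose. Staff working from Section 3.1 or the decision table and a statistician working from Section 8 would act differently with 4 or 5 patients at the lower level. The first group would add none and the second up to three. Adding none leaves fewer than the six that the same table's last row and Section 8 require.

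The terms also differ. Sections 3.1 and 3.1.3 count patients treated, and Section 8 counts patients enrolled. The add-back rule itself does not mention replaced patients or concurrent expansion patients.

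**Working it through.** **Planned sizes.** Three levels of six give 3 × 6 = 18, matching "Up to 18 patients may be required to be enrolled in the 3 cohorts". Two expansions of ten give 18 + 2 × 10 = 38, and 6 + 10 = 16 at each expanded level. All three match the plan. The budget therefore already assumes six escalation patients per level.

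**The three rules side by side.**

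| Already at lower level | Section 3.1 | Section 3.1.3 table | Section 8 | Needed to reach six |
|---|---|---|---|---|
| 3 | 3 | up to 3 | up to 3 | 3 |
| 4 | none | none | up to 3 | 2 |
| 5 | none | none | up to 3 | 1 |
| 6 | none | none | none | 0 |

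The rules part only at 4 and 5. There, the limit of three falls short of six, and Section 8 permits filling to six without fixing the number.

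**How 4 or 5 can arise.** (a) The optional cohort of up to six after 0/3 (Section 3.1) is used in part. This needs no special reading. (b) One or two non-evaluable patients are replaced, so that 4 or 5 are treated to obtain 3 evaluable. This applies only if 'treated' is taken literally.

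**Probability of the sequence.** The documents give no DLT rates, so these are assumptions. With p2 and p3 the rates at levels 2 and 3:

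- P(0/3 at level 2) = (1 − p2)³
- P(level 3 stopped) = 1 − [(1 − p3)³ + 3·p3·(1 − p3)⁵]

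| p2 / p3 | P(0/3) | P(stopped) | Product |
|---|---|---|---|
| 2% / 5% | 0.9412 | 0.0266 | 0.025 |
| 5% / 10% | 0.8574 | 0.0939 | 0.08 |
| 10% / 20% | 0.7290 | 0.2914 | 0.21 |

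Related products point to the low end. Section 1.2.9 reports no DLTs with yeast-brachyury, and Section 1.2.14 reports none in 24 patients given MVA-BN-PRO (one-sided 95% upper bound 1 − 0.05^(1/24) = 11.7%).

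**Probability of the conflict given the sequence.** For (a), the documents do not say how often the optional cohort would be used or stopped at 4 or 5, so the product above is only a ceiling. For (b), with a share q of patients not DLT-evaluable (assumed), P(4 or 5 treated for 3 evaluable) = (1 − q)³(3q + 6q²). This is 0.1415 at q = 5% and 0.4301 at q = 20%. Multiplied by the sequence probability, it gives 0.004 to 0.011, 0.011 to 0.035 and 0.030 to 0.091 for the three pairs of rates.

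These figures cover only a stop at level 3. The same conflict could arise at level 1 if level 2 were stopped.

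**What filling to six could change.** At assumed true DLT rates of 20%, 30% and 40% at the lower level, the chance that the remaining patients bring it to two or more DLTs is:

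- from 1/4: 1 − (1 − p)² = 36%, 51%, 64%
- from 1/5: p = 20%, 30%, 40%
- from 0/4: p² = 4%, 9%, 16%
- from 0/5: zero

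The missing patients can therefore matter, mainly when one DLT has already been seen.

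**The case against.** The best defence is that the plan, read as a whole, already answers the question. Sections 3.1 and 3.1.3 say when to add patients. Neither forbids adding at 4 or 5, so the bar is only implied. The optional cohort in Section 3.1 has no stated time limit and would itself allow a 0/3 cohort to be completed to six. Decisions are planned after the third or sixth patient, so 4 or 5 is not an intended decision point. Most of this stands. It shows that six is the intention, and it identifies which condition is faulty. It does not remove a written condition in the operational text and table that gives a different answer from Section 8.

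Three stronger readings are tempting, and the documents do not support them.

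- A reader might infer that an MTD on 4 or 5 patients would comply with the plan. It would not: the last row of the table, the 1/6 definition and Section 8 all require six.
- A reader might infer that the plan never says who counts. Sections 3.1 and 3.1.3 define the non-evaluable patient and require replacement, and Section 8 treats expansion patients as additional to the six. The gap is only that the add-back rule does not repeat this and uses two different terms.
- A reader might infer that a single concurrent expansion patient at level 2 switches the rule off. That requires counting expansion patients as part of the escalation cohort. The separate escalation and expansion slots in Section 3.1, and the six-then-ten structure in Section 8, point the other way.

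**Conclusion.** The inconsistency is real but minor. The add-back conditions differ at exactly 4 and 5 patients at the lower level, and that state is reachable under the plan's own optional cohort. The remaining provisions show that filling to six is intended, so the limit of three in Sections 3.1 and 3.1.3 is what needs correcting.

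The conflict in wording is certain; how often it would matter is not. The sequence probability of about 0.025 to 0.21 rests entirely on assumed DLT rates, with the related-product experience favouring the low end, and the conflict is less likely than the sequence. The planned maxima of 18 and 38 are unaffected. Team review (Section 7.6.1) and the one-third toxicity rule in Section 8 remain as backstops, though neither settles how the six are to be filled.

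**What to change.** Use one condition in Section 3.1, the Section 3.1.3 table and Section 8, for example: *Enrol at the next lower dose level until six DLT-evaluable escalation-phase patients have been treated there; expansion patients do not count towards these six.* The term DLT-evaluable also settles the position of replaced patients and supplies what Section 8 lacks on replacement. Change the MTD sentence in the Section 3.1.3 text to no more than 1 of 6.

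The cost is amendment wording and at most three further DLT-evaluable escalation patients at one level. These fall within the 18 escalation places and the total of 38. It also takes the time to enrol them plus 28 days of observation before the MTD is declared. Replacing non-evaluable patients is already required, so it adds no new burden.

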### 3.1.1 Dose-Limiting Toxicity

Dose-limiting toxicity will be defined as any one of the following: Any grade  $\geq 3$  hematologic toxicity or grade  $\geq 3$  non-hematologic toxicity that is possibly, probably, or definitely related to study drug, except transient ( $\leq 48$  hour) grade 3 fatigue, local reactions, flu-like symptoms, fever, headache, and laboratory abnormalities that are not associated with organ pathology. Also any  $\geq$  grade 2 allergic and  $\geq$  grade 2 autoimmune reaction(s) (except endocrine-related immune toxicity) will be defined as a DLT. Any grade 3 autoimmune endocrine-related toxicity that has not resolved clinically within 7 days of initiating therapy will also be defined as a DLT.

Generalized erythroderma or macular or papular rash lasting less than 7 days and not associated with desquamation will not be DLTs.

In addition, study accrual will be halted pending discussions with the IRB and the study sponsor if there is an occurrence of a grade 5 toxicity by the NCI-CTCAE (Version 4) attributable to the treatment regimen or if the maximum tolerated dose (MTD) is exceeded in dose level 1.

[figure not shown]
### 3.1.2 DLT Evaluation Period

The evaluation period for DLTs will be 28 days following the first injection of vaccine.

*Abbreviated Title: Phase I MVA-Brachyury-TRICOM*

*Version Date: September 14, 2016*

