**Confidential**

**Abbreviated Title: Phase I MVA-Brachyury-TRICOM****Version Date: September 14, 2016**

physical 						
Medical assessments 	X		X 	X 	X 	X
Imaging	X 				X	X
Urinalysis	X		X	X	X	X
Serum HIV antibody 	X					
Serum hepatitis B & C 	X					
CBC with differential, platelet count	X 		X	X	X	X
Chemistry 	X 		X	X	X	X
EKG	X 				X	X
Correlative / Immunology (blood) 	X		X	X	X	X
ANA titer	X				X	X
CD3, 4, 8, 19 subsets, NK markers and CD4:CD8 ratio	X		X		X	X
HLA typing	X					
Serum beta-HCG 	X					
Pulse oximetry	X					
MVA-brachyury-TRICOM vaccine 		X	X	X		
Adverse events			X	X	X	X
Concomitant medications	X		X	X	X	X

Baseline: H & P and laboratory studies should be completed within 16 days of initiating treatment. Baseline radiographic, EKG, and immunologic studies should be obtained within 28 days of initiating treatment.

Medical assessments: interim history (since last visit), vital signs, physical examination and ECOG performance status. To be performed at baseline, within 3 days of each dose of vaccine and with each restaging visit (about every 85 days on study).

Radiologic studies consisting of CT chest/abdomen/pelvis (and MRI or bone scan when appropriate for tumor type) will be performed within 28 days prior to initiating treatment, on about day 85, and about every 85 days until progression.

Serum HIV antibody should be completed within 8 weeks of initiating treatment.

Serum hepatitis B & C antibody should be completed within 8 weeks of initiating treatment.

Chemistry panel: Na+, K+, Cl, CO2, glucose, BUN, creatinine, albumin, calcium, magnesium, phosphorus, alkaline phosphatase, ALT, AST, total bilirubin, TSH, and LDH.

In females of child-bearing age, beta-HCG to be done at baseline within 48 hours prior to day 1.

Within 3 days prior to each vaccination.

Administered subcutaneously at 1, 2, or 4 sites (days 1, 29, 57 all - 4 days up to +14 days. In the event a dose is delayed, all subsequent doses will be scheduled about 28 days from that dose.)

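### Dose 2 may be given on days 25 to 28, inside the 28-day DLT window, and no rule requires the Day 29 safety checks to be reviewed before escalation or expansion

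*Combined protocol and SAP*

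**What the plan says.** **Window and trigger.** Section 3.1.2: "The evaluation period for DLTs will be 28 days following the first injection of vaccine". Section 3.1 says that toxicity in this period drives escalation and the MTD estimate. Section 8 gives the trigger for opening the next level: "If 0/3 have a dose limiting toxicity (DLT) after 28 days from the third patient receiving the initial vaccine on study". Section 3.1 opens the expansion cohorts on the same basis, from patients "treated at that dose level and have not experienced a DLT for at least 28 days". A patient without a DLT who does not complete the 28 days is replaced (Sections 3.1 and 3.1.3).

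**Scheduled checks.** After dose 1 there is a 2-hour observation (Section 3.1). In the Section 3.3 calendar, the next adverse-event, CBC and chemistry entries are in the Day 29 column, which also holds dose 2. The following ones are at Day 57.

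**Timing of dose 2.** Footnote 9, on the vaccine row, allows "days 1, 29, 57 all - 4 days up to +14 days". Section 3.1 agrees; the précis gives 28 ± 4 days. The medical assessment (interim history, vital signs, examination, performance status) follows the dose. Footnote 2 reads "To be performed at baseline, within 3 days of each dose of vaccine and with each restaging visit" and footnote 8 reads "Within 3 days prior to each vaccination". No footnote gives a window for the Day 29 adverse-event, CBC or chemistry entries. Section 2.3.1 places a different blood test, the lymphocyte subsets, "about day 29 prior to vaccination".

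**What counts.** Section 3.1.1 makes hematologic toxicity of grade 3 or higher a DLT. It exempts some events, among them laboratory abnormalities without organ pathology.

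**The concern.** The window and the dosing allowance overlap, with three possible consequences.

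- **Re-dosing.** Section 3.4.1 stops vaccine in a patient with a DLT. A patient given dose 2 on day 25 receives it with 4 days of the window still to run.
- **Attribution.** A reaction to an early dose 2 that starts by day 29 falls, by time, in a window meant to describe dose 1. The plan does not say how to attribute it.
- **Decision on incomplete data.** The escalation, evaluability and expansion rules are written in elapsed days, and none names a visit or result. Each decision rests on 3 to 6 patients, so one event changes the action: 0 of 3 against 1 of 3, or 1 of 6 against 2 of 6. A hematologic DLT may show only on a blood test, and this is a first-in-human trial.

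**Working it through.** The plan gives no figure of its own on this point. The check is day arithmetic, with dose 1 on day 1.

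**Inputs.** Window: 28 days (Section 3.1.2). Dose 2: day 29, −4 to +14 days (Sections 3.1 and 3.3). Medical assessment: up to 3 days before the dose (footnote 8).

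**1. Window and dosing range.** The window closes on day 1 + 28 = 29. Dose 2 runs from 29 − 4 = day 25 to 29 + 14 = day 43, which is 43 − 25 + 1 = 19 permitted days. Of these, 4 are early (25–28), 1 is on time (29) and 14 are late (30–43).

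**2. Early dosing, no assumption needed.** Dose 2 on day d leaves 29 − d days of the window: 4, 3, 2 and 1 for days 25, 26, 27 and 28. If day 1 is counted as the first of the 28 days, the window ends with day 28. Days 25–28 still lie inside it, with 28 − d = 3, 2, 1 and 0 further days.

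**3. Adverse-event and laboratory checks.** The result depends on whether they move with dose 2.

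| Dose 2 on | Checks move with dose 2 | Checks stay on day 29 |
|---|---|---|
| Days 25–28 | Last 4 to 1 of 28 days (14% to 4%) not reviewed by day 29 | No gap |
| Day 29 | Complete | No gap |
| Days 30–43 | Complete, but 1 to 14 days after day 29 | No gap |

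The percentages are 4/28 = 14% and 1/28 = 4%. The late case matters only if the team escalates before that visit, so it mainly concerns the last patient in a cohort. The early case can affect any escalation patient.

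**4. Medical assessment, which does move.** For dose 2 on day d it may be as early as day d − 3, which is 29 − (d − 3) = 32 − d days before the window closes. For d = 25 to 31 that is 7, 6, 5, 4, 3, 2 and 1 days, on 7 of the 19 permitted days. From d = 32 it cannot precede closure.

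**5. Sensitivity to the précis.** With ± 4 days, dose 2 falls on days 25–33, which is 9 days: 4 early, 1 on time, and 4 late by 1 to 4 days. The early overlap is unchanged.

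These are counts of permitted days, not frequencies or risks.

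**The case against.** The strongest reply is that a team following the plan would look at the Day 29 checks anyway. Section 3.1 bases decisions on 28-day toxicity. Section 8 asks for 0 of 3 with a DLT, which is a finding and not only a date. Section 7.6.1 bases escalation on toxicity data from prior patients, has the principal investigator review each patient's adverse events, and sets team meetings at least every other week. Serious adverse events go to the sponsor immediately (Section 7.3). This largely stands: the missing results requirement is partly an argument from silence. But none of these rules says that the window's data must be complete. Section 6.1.1 allows 10 business days for data entry, and an unmeasured laboratory toxicity generates no report.

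A reader might infer that early dosing always leaves an adverse-event or laboratory gap. The documents do not support that. Footnote 9 belongs to the vaccine row, and if the checks stay on day 29 the gap disappears. The Section 2.3.1 wording on lymphocyte subsets makes it natural to read the checks as moving with the dose, but does not establish it.

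Early dosing does not shorten the DLT clock, and counting a dose 2 reaction errs on the cautious side. That is fair, but it can also charge a dose level with toxicity that needed two doses.

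The laboratory exemption in Section 3.1.1 narrows the set of laboratory-only DLTs. Whether it reaches hematologic toxicity is unclear from the sentence, and applying it still requires a result.

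Two further points stand. Most events in earlier MVA trials resolved within 48 hours, and a related MVA-BN vector had no DLTs in 24 patients (Section 1.2.14). Also, one CBC on day 29 would not show a toxicity that came and went earlier.

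**Conclusion.** The point holds in a limited form. Without any assumption, the plan permits dose 2 on 4 days before the DLT window closes, and no rule makes the Day 29 checks a precondition for counting a patient as DLT-free or for opening the next level or expansion.

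On the assumption that the checks move with dose 2, an early dose leaves the last 1 to 4 days unreviewed at the earliest decision point, and a late dose can put the last patient's first post-dose laboratory results up to 14 days after it. If they stay on day 29, only early dosing and the missing requirement remain.

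A reader might infer that the plan lets the team escalate without regard to toxicity, or that a wrong escalation is likely. Neither follows: escalation is tied to toxicity data, and the documents give no basis for a probability. The practical risk is small. The change is still worth making because a single event decides each step and the remedy is cheap.

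**What to change.** Add to Sections 3.1.2 and 3.3, for dose-escalation patients only:

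> Dose 2 is not given before day 29. The Day 29 adverse-event review, CBC and chemistry are done on or after day 29, whenever dose 2 is given, and are reviewed before the patient counts as DLT-free and before the next dose level or expansion opens.

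When dose 2 is on time, the checks are done at that visit, before the injection. The first sentence protects the individual patient and keeps dose 2 reactions out of the early-dosing overlap; the second protects the escalation decision.

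**Cost.** The −4 day allowance is lost for dose 2 in up to 3 × 6 = 18 patients. If dose 2 is delayed to days 30–43, either escalation waits 1 to 14 days for that visit, or the checks are done at one separate visit from day 29. The change does not add a blood test between day 1 and day 29, so it would not detect a laboratory toxicity that had already recovered.
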